3.3 Discontinuation from Study Treatment

Patients will be discontinued from study treatment for any of the following reasons:

- Relapse of underlying malignancy
- Irreversible or intolerable toxicity or abnormal laboratory values thought to be related to drug toxicity
- The patient is unable to tolerate itacitinib at a dose of 100 mg QD.
- Additional systemic therapy is required for GVHD progression or lack of response, including corticosteroid doses greater than those used on Study Day 1.
- Conditions requiring therapeutic intervention not permitted by the protocol
- Intercurrent illness (this will be at the Investigator's discretion)
- Inability of the patient to comply with study requirements
- Patient requests to discontinue treatment, but agrees to finish study procedures
- Patient withdraws consent from the study and is discontinued from the study
- Non-compliance/lost to follow-up
- Pregnancy
- Further participation would be injurious to the patient's health or well-being, in the Investigator's medical judgment.
- The study is terminated by the Sponsor or the Institutional Review Board (IRB).

After discontinuation from protocol treatment, patients must be followed for AEs for 30 days after their last dose of study drug. All new AEs occurring during this period must be reported and followed until resolution, unless, in the opinion of the Investigator, these values are not likely to improve, because of the underlying disease. In this case, the Investigator must record his or her reasoning for this decision in the patients' medical records.

All patients who have Grade 3 or 4 laboratory abnormalities (per National Cancer Institute Common Terminology Criteria for Adverse Events [NCI CTCAE] Version 5) at the time of discontinuation must be followed until the laboratory values have returned to Grade 1 or 2, unless it is, in the opinion of the Investigator, not likely that these values will improve. In this case, the Investigator must record his or her reasoning for making this decision in the patients' medical records.

4. STUDY REGISTRATION

The patient must willingly consent after being informed of the procedures to be followed, the experimental nature of the treatment, potential benefits, treatment alternatives, risks, and discomforts. Human protection committee (IRB) approvals of this protocol and any associated ICFs is required. Eligible patients who wish to participate in the study will be enrolled into the study.

CONFIDENTIAL

STUDY DRUG: INCB039110 (ITACITINIB)
FINAL PROTOCOL DATE: 26 OCTOBER 2021

INNOVATIONS STUDY NUMBER: BMT 29
VERSION 4

Registration must occur prior to the initiation of protocol therapy. Patients eligible to participate in the study may be enrolled by each site following the patient registration instructions provided by the Sarah Cannon Development Innovations (Innovations) study contact. Patient registration follow-up and/or confirmation will be provided via email within approximately 24 hours or by the next business day.

5. STUDY DESIGN

This is an open-label, multi-center, single-arm pilot study in patients who have been receiving immunosuppressive therapy for the treatment of cGVHD for a duration of >6 months prior to starting daily itacitinib treatment in this study. The planned enrollment for this study is 40 patients, and patient treatment is expected to be approximately 12 months, although patients seeing clinical benefit may stay on treatment for an additional year.

Patients will continue to receive their systemic immunosuppressive regimen for SR-cGVHD per standard of care as determined by the Investigator during the screening and treatment periods. In addition, transfusion support, continued use of anti-infective medications, and topical steroid therapy is permitted.

Chronic GVHD staging and grading will be assessed for efficacy as per NIH Consensus Criteria (Jagasia et al. 2015). Safety and tolerability will be assessed as per NCI CTCAE Version 5.

5.1 Main Treatment Periods

Patients who taper off study treatment and all immunosuppressive therapy due to achieving a cGVHD status of CR or PR will continue to be followed according to the Schedule of Assessments (Appendix D), including all safety and efficacy assessments, and will be monitored for cGVHD recurrence.

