5.1.2 Extension Period (Cycle 8 to Cycle 12)

Patients will continue treatment and will be monitored on Day 1 of each cycle until the end-of-treatment (EOT) visit, according to the assessments outlined in Appendix D.

Patients undergoing dose tapering should be monitored for cGVHD flare occurrences, which must be reported in the database.

CONFIDENTIAL

STUDY DRUG: INCB039110 (ITACITINIB)
FINAL PROTOCOL DATE: 26 OCTOBER 2021

INNOVATIONS STUDY NUMBER: BMT 29
VERSION 4

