6.3 Study Assessment Timing

The treatment period begins on the day the patient receives the first dose of study drug through the point at which the Investigator determines the patient will be permanently discontinued from study drug. Dates for subsequent study visits will be determined based upon this day and should occur as close to the scheduled day as possible taking into consideration the windows of time included in the assessments table. During the Day 1 visit, results from screening visit evaluations should be reviewed to determine whether the patient continues to meet the eligibility requirements as specified in the protocol.

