6.6.2 Survival Follow Up (Every 3 Months [\pm 30 Days])

Patients who permanently discontinue the study treatment for reasons other than achieving a GVHD status of CR or PR will be followed for survival, relapse of underlying malignancy, and reporting of new cGVHD therapies approximately every 3 months for 1-year after completion of study drug, and can be contacted by telephone, email, or by a site visit.

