Appendix D: BMT 29 Schedule of Assessments

Study Period	Screening	Treatment Period							Follow-Up		
		Cycle 1				Cycles 2 to 6	Cycle 7	Cycles 8+			
Cycle ^a											
Visit Day	Day -28 to -1 ^b	1	8	15	22	1 (± 7 days)	1 (± 7 days)	1 (± 7 days)		(± 7 days)	Every 3 months (± 1 month)
Informed consent	X										
Inclusion / exclusion criteria	X										
Medical history and demographics ^c	X										
Physical examination ^{c,d}	X	X	X	X	X	X	X	X	X	X	
ECOG performance status ^{c,d}	X	X				X	X	X	X	X	
Vital signs ^c	X	X	X	X	X	X	X	X	X	X	
Blood transfusion review ^d	X	X				X	X	X	X		
12-Lead electrocardiogram ^c	X								X		
Pulmonary function test ^d	X					X (C4 only)	X				
Urine pregnancy test ^{c,e}	X	X				X	X	X	X	X	
Safety laboratory (hematology, lipids [fasting], and chemistries) ^c	X	X	X	X	X	X	X	X	X	X	
Safety laboratory (urine) ^c	X	X	X	X	X	X	X	X	X	X	
Virology testing ^f	X										
Concomitant medication review	X	X	X	X	X	X	X	X	X	X	
Adverse events and infection monitoring	X	X	X	X	X	X	X	X	X	X	
cGVHD diagnosis and staging	X										
Clinician-reported global cGVHD activity assessment ^g		X				X	X	X	X		

CONFIDENTIAL

INNOVATIONS STUDY NUMBER: BMT 29

VERSION 4

STUDY DRUG: INCB039110 (ITACITINIB)
FINAL PROTOCOL DATE: 26 OCTOBER 2021

Study Period	Screening	Treatment Period						Follow-Up		
		Cycle 1			Cycles 2 to 6	Cycle 7	Cycles 8+	EOT ^k	30-Day Safety FU ^l	FU for Survival ^m
Cycle ^a		1	8	15	22	1 (± 7 days)	1 (± 7 days)	1 (± 7 days)	(± 7 days)	Every 3 months (± 1 month)
Visit Day	Day -28 to -1 ^b									
Patient-reported global cGVHD activity assessment ^g		X				X	X	X	X	
Assessment of cGVHD response (NIH criteria) ^h						X	X	X ^h	X	
Chimerism assessment (institutional standards)	X									
Lee Symptom Scale ⁱ	X	X					X		X	
Document corticosteroid dosage (total dose/kg and type of corticosteroid)	X	X	X	X	X	X	X	X	X	
Document concomitant cGVHD therapies	X	X	X	X	X	X	X	X	X	
Assess underlying disease relapse ^j		X				X	X	X	X	X
New cGVHD therapies										X X
Dispense/collect study drug		X				X	X	X	X	
Patient status										X

Itacitinib Schedule of Assessments Footnotes

- a Treatment cycles are 28 days (4 weeks). Patients will continue treatment with itacitinib for up to 24 months or until patients discontinue from study treatment for any of the following reasons listed in Section 3.3.
- b Screening should take place within 28 days of start of study treatment.

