- d Physical examinations including the measurements of height (screening only) and weight will be done at screening, on Days 1, 8, 15, and 22 of Cycle 1, on Day 1 of each subsequent treatment cycle, at the end-of-treatment (EOT) and the 30-day safety follow-up (FU) visits, and at the discretion of the Investigator. Blood transfusions will be reviewed at screening, on Day 1 of each cycle, and at the EOT visit. ECOG performance status will be done at the visits noted in the table. Pulmonary function test will be performed at screening (within 14 days of C1D1) and on Day 1 of Cycle 4 and Cycle 7 and include FEV1, FVC, DLCO (corrected for Hb), TLC and RV (see Section 6.7.3).
- e A urine pregnancy test must be done at screening (3 days prior to initiation of treatment) for women with child-bearing potential, Day 1 of each cycle, at the EOT visit, and at the 30-day safety follow-up visit. Additional pregnancy testing is at the Investigator's discretion. Positive results are to be confirmed with serum beta human chorionic gonadotropin testing.

CONFIDENTIAL

INNOVATIONS STUDY NUMBER: BMT 29

VERSION 4

- f Virology tests to include: HIV, Hepatitis B surface antigen, Hepatitis B surface antibody, Hepatitis B core antibody, Hepatitis C antibody, HBV-DNA (if required), HCV-RNA (if required)
- g Patients will be assessed for severity of cGVHD using the Clinician-Reported Global cGVHD Activity Assessment Form (see Appendix E) and Patient-reported cGVHD Activity Assessment Form (Appendix F) on Day 1 of each cycle, and at the EOT visit. If a patient withdraws from treatment due to reasons other than PD, GVHD grading will be repeated at this visit.
- h Response criteria (CR, PR, or progression) based on the 2014 NIH Consensus Development Project on Clinical Trials in cGVHD (see Appendix H for criteria) will be assessed on Day 1 of Cycles 2 through 7; and then every odd-numbered cycle thereafter starting on Day 1 of Cycle 9, as well as the EOT visit.
- i The Lee Symptom Scale (see Appendix I) will be used to capture changes in health status during the course of treatment relative to screening and will be done at screening, on Cycle 1 Day 1, Cycle 7 Day 1, and at the EOT visit. If a patient stops study drug before 6 months, the form should be filled out at that time.

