- j Participants will be closely monitored for any evidence of underlying disease relapse or recurrence on Day 1 of each cycle, at the EOT, and the survival follow-up visit. A formal re-staging is not required. Re-staging will be done at the Investigator's discretion. The date of malignant and non-malignant hematologic disease relapse and subsequent management should be collected on the appropriate eCRF.
- k An EOT visit should be performed for all patients who permanently discontinue study treatment (preferably within 7 days and no later than 14 days after the last treatment of study drug). If the EOT visit coincides with a regular study visit, the EOT evaluations will supersede those of that scheduled visit, and the data should be entered in the EOT visit in the eCRF (see Section 6.5).
- l A safety follow-up visit will be done 30 days (± 7 days) following end of treatment. Adverse events and SAEs must be reported for least 30 days after the last dose of study drug, and must be followed until toxicities resolve, return to baseline, or are deemed irreversible, whichever is longer (see Section 6.6.1).
- m Follow-up for survival: patients will be followed for survival after treatment has been discontinued. Patients should be contacted by telephone, email, or visit every 3 months for 1-year after their last dose of study treatment to assess for new GVHD therapy, relapse of underlying malignancy and survival status until death, withdrawal of consent, or the end of the study, whichever occurs first (see Section 6.6.2).

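### Conflicting rules on when cGVHD follow-up ends for responders who taper off all therapy leave the recurrence objective dependent on which rule a site follows

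*Combined protocol and SAP*

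**What the plan says.** Recurrence or progression of cGVHD is a secondary objective (section 2.2), as is overall survival. The provisions that decide how long a responder is observed after stopping drug are these.

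- **Section 5.1.** Patients who come off study drug and all immunosuppression because of CR or PR remain on Appendix D, "including all safety and efficacy assessments, and will be monitored for cGVHD recurrence". No end date is given.
- **Section 5.1.2.** In the extension period patients are "monitored on Day 1 of each cycle until the end-of-treatment (EOT) visit".
- **Section 6.3.** The treatment period runs from the first dose "through the point at which the Investigator determines the patient will be permanently discontinued from study drug".
- **Appendix D, footnote k.** "An EOT visit should be performed for all patients who permanently discontinue study treatment". The footnote makes no exception for responders.
- **Appendix D table and footnotes g and h.** The two global activity forms (Appendices E and F) fall on Day 1 of each cycle and at EOT. The NIH response assessment (Appendix H) is done at Cycles 2 to 7 and then "every odd-numbered cycle thereafter starting on Day 1 of Cycle 9, as well as the EOT visit". Neither is marked in the 30-day safety or survival follow-up columns.
- **Section 6.6.2.** "Patients who permanently discontinue the study treatment for reasons other than achieving a GVHD status of CR or PR will be followed for survival", with relapse and new cGVHD therapy also asked about, every 3 months for a year.
- **Appendix D, footnote m.** "patients will be followed for survival after treatment has been discontinued", again with no exception for responders. Section 5.3 likewise promises a year of survival follow-up after the last dose without exempting anyone.

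**The concern.** A patient who stops itacitinib in response, already off other immunosuppression, is among the best responders in the trial. The period after stopping is when that patient's recurrence or freedom from recurrence tells most about durability. The protocol gives two answers on whether cGVHD is still scored in that period, and two answers on whether the patient is contacted for survival.

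Section 10.4.2 defines only the response rate and overall survival. It gives no definition of recurrence, no time origin and no censoring rule. The visit schedule alone therefore decides which recurrences are seen. If sites resolve the conflict differently, the recurrence summary mixes patients scored well beyond drug withdrawal with patients last scored at EOT, and some events may go unrecorded.

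**Working it through.** **1. The plan's own figure.** Section 10.2 gives a width of 0.266 for the exact 95% interval with N = 40 and a proportion of 0.200, which is 8 responders (0.20 × 40).

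- Lower limit: Beta quantile(0.025; 8, 33) = 0.0905
- Upper limit: Beta quantile(0.975; 9, 32) = 0.3565
- Width: 0.3565 − 0.0905 = 0.2660

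The stated width is reproduced. The present point does not change it.

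**2. Is stopping for CR/PR a permanent discontinuation?** If it were not, footnote k would not apply and the conflict would disappear. But section 6.6.2 separates permanent discontinuation for other reasons from permanent discontinuation on achieving CR or PR. It thus treats the second as one kind of permanent discontinuation. Footnote k and the end of the treatment period in 6.3 then apply to these patients.

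**3. What is scheduled after EOT?** Appendix D marks no Appendix E, F or H assessment after EOT. The only cGVHD item in the follow-up columns is new cGVHD therapy. Section 5.1.2 asks for flares to be recorded during dose tapering, which does not cover the time after the last dose.

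**4. The same patient under each set of rules.**

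| Rules followed | cGVHD scoring after drug stops | Survival and new-therapy information |
|---|---|---|
| 5.1 | Continues on Appendix D, end undefined | Obtained at the visits |
| 5.1.2, footnote k, 6.6.2 | Last at EOT | Last scheduled contact is the 30-day visit (30 ± 7, so days 23 to 37) |
| 5.1.2, footnote k, footnote m | Last at EOT | Every 3 months for 1 year (12/3 = 4 contacts); recurrence seen only as new GVHD therapy |

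The second row also touches overall survival. Section 10.4.2 censors at the last date known alive, so a CR/PR stopper handled this way could be censored about a month after the last dose, against the year promised in 5.3.

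**5. Size.** The documents give no rate of coming off all therapy and no recurrence rate, so the number of missed events cannot be derived. What can be shown is the weight of one missed event in a crude proportion among responders:

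- 20% response rate (the plan's illustration): 8 responders, 1/8 = 12.5 points
- 50% (assumed): 20 responders, 1/20 = 5 points
- 80% (assumed): 32 responders, 1/32 = 3.1 points

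**6. The primary endpoint.** Section 8.3 allows the itacitinib taper after 6 months in CR or PR, with corticosteroids stopped for at least 8 weeks; an earlier taper needs Study Chair approval. The primary assessment is at Cycle 7 Day 1 (section 5.1.1). Most of the affected follow-up therefore comes after it.

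**The case against.** The best defence is that 5.1 is the specific rule for this subgroup and should govern. Appendix D has an open-ended column for Cycles 8 and later that carries the response assessment and both global forms. The exemption in 6.6.2 fits that reading: these patients need no 3-monthly contacts because they are still seen every cycle. This stands as evidence of intent, and a site that follows it loses nothing.

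A reader might infer that 6.3 and footnote k themselves cancel later cGVHD visits. They do not. Section 6.3 defines the treatment period, and footnote k requires an EOT visit without saying that nothing follows. The conflict comes from 5.1.2, which ends cycle monitoring at EOT, together with the absence of any post-EOT cGVHD assessment in Appendix D and of any column for responders off drug.

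A site that ends cycle visits but follows footnote m would also still hear of a treated recurrence within a year of the last dose. That limits the loss, but such an event has no NIH score, and an untreated recurrence could pass unnoticed.

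Finally, this is an exploratory single-arm pilot with no hypothesis test, and the affected group may be very small. That bears on priority. It does not remove the contradiction.

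**Conclusion.** The point holds as a conflict between stated rules on a secondary objective. Recurrence after drug withdrawal would rest on follow-up that could differ by site, and one permissible reading leaves these responders with neither cGVHD scoring nor survival contacts after the 30-day visit. It should be corrected, but the 6-month response rate, N and the interval width are not materially affected.

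Two stronger readings are tempting and not supported:

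- **That durability will be overstated whichever rule sites follow.** Under 5.1 there is no loss. Missed events can only lower a crude recurrence proportion, but the plan specifies no such estimator. In a Kaplan-Meier analysis, which section 10.4 uses for time-to-event endpoints, early censoring of the best responders could bias in either direction.
- **That the bias can be given as a range.** Assuming, for example, that 2 to 6 of 8 responders come off all therapy and that 20% to 60% of them recur gives 2 × 0.2 = 0.4 to 6 × 0.6 = 3.6 events, or 5 to 45 points. Neither input is in the documents, and the sum supposes that every such recurrence is missed, contrary to 5.1 and footnote m.

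The supportable statement is 12.5 points per missed event, assuming the plan's illustrative 20% response rate and all 40 patients evaluable.

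**What to change.** Reconcile sections 5.1, 5.1.2, 6.3, 6.5 and 6.6.2 with Appendix D footnotes g, h, k and m, so that one rule applies to patients who stop because of CR or PR:

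- They complete the EOT forms but stay on the existing Appendix D schedule, with Appendices E and F on Day 1 of each cycle and Appendix H at odd-numbered cycles, up to one end date that the sponsor states. Appendix D should show this in its own column or footnote.
- Section 10.4.2 should define recurrence and censor it at the last Appendix H assessment. It should also say how a recurrence known only through new cGVHD therapy is counted.
- Section 6.6.2 should be aligned with footnote m and section 5.3, so that these patients also have survival and new-cGVHD-therapy contacts.

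The change concerns assessments and analysis only. Its cost is wording plus a few extra visits in a few patients. Section 5.1 already calls for such visits, although without an end date, so the date chosen sets how many.

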5.1.1 Primary Efficacy Period (Cycle 1 through End of Cycle 6)

The primary efficacy period is defined as Cycle 1 through the end of Cycle 6. A cycle is 28 days. Study treatment will begin on Cycle 1 Day 1 and study drug will be dispensed on Day 1 of each cycle.

Patients will be treated for a minimum of 6 cycles, unless they meet the discontinuation criteria listed in Section 3.3).

Primary efficacy assessments will be performed on Cycle 7 Day 1, after completion of 6 cycles of treatment.

5.1.2 Extension Period (Cycle 8 to Cycle 12)

Patients will continue treatment and will be monitored on Day 1 of each cycle until the end-of-treatment (EOT) visit, according to the assessments outlined in Appendix D.

Patients undergoing dose tapering should be monitored for cGVHD flare occurrences, which must be reported in the database.

CONFIDENTIAL

STUDY DRUG: INCB039110 (ITACITINIB)
FINAL PROTOCOL DATE: 26 OCTOBER 2021

INNOVATIONS STUDY NUMBER: BMT 29
VERSION 4

5.2 Treatments

5.2.1 Itacitinib

Itacitinib will be administered orally at a starting dose of 200 mg once QD (2 x 100 mg tablets), and may be taken with or without food.

Itacitinib dose will be increased to 300 mg QD (3 x 100 mg tablets) for patients with no response (NR)/stable disease (SD) after 2 months of therapy at 200 mg QD.

Patients may have dose reductions or interruptions of itacitinib during the course of treatment based on AEs, clinical evaluation, and laboratory assessments. See Section 8.1 for dose modifications of study drug.

5.2.2 Dietary Restrictions

Patients should be instructed to refrain from the consumption of pomegranates or pomegranate juice, and grapefruit or grapefruit juice, as these are known to inhibit cytochrome CYP3A enzymes and may increase exposure to itacitinib.

5.2.3 Corticosteroids

Patients will join this study after receiving immunosuppressive regimens for SR-cGVHD for at least 6 months and will remain on the dose at which they started if considered clinically appropriate by the Investigator.

Corticosteroids should be tapered per institutional guidelines at a rate that is commensurate with resolution of GVHD manifestations. If GVHD flares during the taper of prednisone or methylprednisolone, the dose may be re-escalated at the Investigator's discretion and will not be considered treatment failure, as long as the dose does not exceed the initial starting dose. If the dose required exceeds this threshold, or if the flare is not responsive to increased corticosteroids or multiple flares are observed, then the patient will be considered to have experienced treatment failure and will be withdrawn from study treatment.

